6.1.5 Hypertension toxicity

Therapeutic BP monitoring by a health care provider will occur every 2 weeks during the first 2 cycles then at least every cycle for the duration of treatment in the dose escalation phase, and on D1 and D8 of cycle 1 then at least every cycle in the expansion phase. All patients will be required to monitor their BP at least once a day (preferably BID) throughout the treatment and record the readings in the study diary ([Appendix E](#)). Table 3 will be used for the grading of pazopanib-associated hypertension, for immediate and long-term management, and for the determination of pazopanib dose modification. Suggested antihypertensive medications are listed in Table 4.

Table 3: Recommended Hypertension Monitoring and Management (BP in mmHg)

Grade (CTCAE v4)	Antihypertensive Therapy	Blood Pressure Monitoring	Pazopanib Dose Modification
Persistent Grade 1 Pre-hypertension Systolic 120-139 Diastolic 80-90		Standard	No Change
Persistent Grade 2-Moderate Systolic 140-159 Diastolic 90-99	
Step 1) Initiate BP treatment and if needed, after 24-48 hr of treatment, increase dose in stepwise fashion every 24-48 hours until BP is controlled or at maximum dose of medication
 
Step 2) If BP still not controlled, add another anti-hypertensive medication, a LA DHP CCB, ACE1, ARB, or ABB; increase dose of this drug as described in step 1
 
Step 3) If BP still not controlled, add 3rd drug from the list of antihypertensives in step 2; increase dose of this drug as described in step 1
 
Step 4) If BP still not controlled, consider either 1 dose reduction of pazopanib or stopping pazopanib
	BP should be monitored as recommended by the treating physician	No change except as described in step 4

Grade (CTCAE v4)	Antihypertensive Therapy	Blood Pressure Monitoring	Pazopanib Dose Modification
	
NOTE: Stopping or reducing the dose of pazopanib is expected to cause a decrease in BP. The treating physician should monitor the subject for hypotension and adjust the number and dose of antihypertensive medication(s) accordingly
		

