
Persistent Grade 3 Severe Systolic ≥ 160 Diastolic ≥ 100
	
HOLD pazopanib until systolic BP ≤ 159 and diastolic BP ≤ 99.
 
BP management is identical to that for Grade 2 (see steps 1-4 above) with 2 major exceptions:
 
1) If systolic BP >180 or diastolic BP >110 and the subject is symptomatic: optimal management with intensive IV support in ICU; STOP pazopanib and notify hospital staff that stopping pazopanib may result in a decrease in BP and
 
2) If systolic BP >180 or diastolic BP >110 and the subject is asymptomatic, 2 new antihypertensives must be given together in step 1 (and dose escalated appropriately as in step 1).
 
NOTE: Stopping or reducing the dose of pazopanib is expected to cause a decrease in BP. The treating physician should monitor the subject for hypotension and adjust the number and dose of antihypertensive medication(s) accordingly
	
BP should be monitored as recommended by the treating physician unless the subject is symptomatic with systolic BP >180 or diastolic BP >110 in which case, monitoring should be intensive.
	
HOLD pazopanib until systolic BP ≤ 159 and diastolic BP ≤ 99. After this, pazopanib may be re-administered. If BP is still grade 2, manage as described above for grade 2 hypertension.
 
In most circumstances, if BP cannot be controlled after an optimal trial of antihypertensive medications, consider either 1 dose reduction of pazopanib when systolic BP ≤ 159 and diastolic BP ≤ 99 or stopping pazopanib.
 
HOWEVER, If the subject requires hospitalization for management of symptomatic systolic BP >180 or diastolic BP >110, permanently discontinue pazopanib or if BP is controlled to systolic BP ≤ 159 and diastolic BP ≤ 99, consider re-starting pazopanib at 1 lower dose level after consultation with the study Principal Investigator

Grade 4 Life-threatening consequences of hypertension
	
Optimal management with intensive IV support in ICU; STOP pazopanib and notify hospital staff that stopping pazopanib may result in a decrease in BP
	
Intensive
	
Permanently discontinue pazopanib or if systolic BP ≤ 159 and diastolic BP ≤ 99, consider re-starting pazopanib at 1 lower dose level after consultation with the study Principal Investigator

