
Abbreviations: Dihydropyridine calcium-channel blockers (DHP-CCB), selective beta blockers (BB), Angiotensin Converting Enzyme Inhibitors (ACEI), Angiotensin II Receptor Blockers (ARB), alpha beta blocker (ABB)
 
 *See table below for suggested antihypertensive medications by class 			

Grade (CTCAE v4)	Antihypertensive Therapy	Blood Pressure Monitoring	Pazopanib Dose Modification
	
 • If subjects require a delay of >2 weeks for management of hypertension, discontinue protocol therapy • If subjects require >2 dose reductions, discontinue protocol therapy • Subjects may have up to 2 drugs for management of hypertension prior to any dose reduction in pazopanib • 24-48 hours should elapse between modifications of antihypertensive therapy • Hypertension should be graded using CTCAE v4 		

Notes:

- While patients are receiving treatment with pazopanib, the early initiation of antihypertensive treatment for grade 1 or 2 hypertension to minimize more severe or persistent hypertension is not considered a grade 3 adverse event.
- Decisions to hold or decrease the pazopanib dose during treatment must be based on BP readings taken in the clinic by a medical professional.
- Based on prior clinical experience with pazopanib, the use of calcium channel blockers (dihydropyridine category) and ACE inhibitors as first-line and second-line therapy is recommended.

Table 4: Oral Antihypertensive Medications: Agents in bold characters are suggested as optimal choices to avoid or minimize potential drug-interactions with pazopanib through CYP450.

Agent class	Agent	Initial dose	Intermediate dose	Maximum dose	Hepatic metabolism
Dihydro-pyridine Calcium-Channel Blockers (DHP CCB)	nifedipine XL	30 mg daily	60 mg daily	90 mg daily	CYP 3A4 substrate
	amlodipine	2.5 mg daily	5 mg daily	10 mg daily	CYP 3A4 substrate
	felodipine	2.5 mg daily	5 mg daily	10 mg daily	CYP 3A4 substrate and inhibitor
Selective β Blockers (BB)	metoprolol	25 mg twice daily	50 mg twice daily	100 mg twice daily	CYP 2D6 substrate
	atenolol	25 mg daily	50 mg daily	100 mg daily	No
	acebutolol	100 mg twice daily	200-300 mg twice daily	400 mg twice daily	Yes (CYP450 unknown)
	bisoprolol	2.5 mg daily	5-10 mg daily	20 mg daily	Yes (CYP450 unknown)
Angiotensin Converting Enzyme Inhibitors (ACEIs)	captopril	12.5 mg 3x daily	25 mg 3x daily	50 mg 3x daily	CYP 2D6 substrate
	enalapril	5 mg daily	10-20 mg daily	40 mg daily	CYP 3A4 substrate

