APPENDIX E: PATIENT'S MEDICATION DIARY

EXPANSION PHASE, COHORT A, CYCLE 1

Today's date _____

Agent: Pazopanib, ARQ 197

Patient Name _____

Patient Study ID _____

INSTRUCTIONS TO THE PATIENT:

1. Complete one form for each cycle of treatment.
2. **Starting on day 1**, you will take **pazopanib** once each day in the morning either 1 hour before or 2 hours after a meal with 1 cup of water.
Dose: _____. Take ____ 200 mg tablets and ____ 400 mg tablets every day. You should swallow the tablets whole.
Do not chew, crush, or break the tablets.
3. **Starting on day 8**, you will take **ARQ 197** twice each day, about 12 hours apart, with food. You should swallow the tablets whole. **Do not chew, crush, or break the tablets. You will not take ARQ 197 on days 1-7 of cycle 1.**
Morning dose: _____. Take ____ 120 mg tablets. Evening dose: _____.
Take ____ 120 mg tablets.
4. Record the date, the number of tablets of each size you took, and when you took them.
5. If you have any comments or notice any side effects, please record them in the Comments column.
6. Please bring this form and your bottles of **pazopanib and ARQ 197** tablets when you return for each appointment.
7. You should measure your own blood pressure at home at least once a day (preferably twice a day). If your systolic pressure (top number) is greater than 150 or your diastolic blood pressure (bottom number) is greater than 90, re-measure your blood pressure 1 to 4 hours later. If your systolic pressure is still greater than 150 or your diastolic blood pressure is still greater than 90, please contact your study team for instructions. You should also call the research team if you experience any symptoms of high blood pressure, such as chest pain, shortness of breath, headache, blood in the urine, or double vision.

CTEP Protocol #8880
 Clinical Center Protocol #: 12-C-0009

CTEP-assigned Protocol #8880 Local Protocol # _____
--

Today's date _____
 Patient Name _____

Agent: Pazopanib, ARQ 197
 Patient Study ID _____

Day	Date	Pazopanib		ARQ 197				Blood Pressure AM	Blood Pressure PM	Comments	
		Time of dose	# of tablets taken		Time of morning dose	# of tablets taken	Time of evening dose				# of tablets taken
			200 mg	400 mg							
1				-----	-----	-----	-----				
2				-----	-----	-----	-----				
3				-----	-----	-----	-----				
4				-----	-----	-----	-----				
5				-----	-----	-----	-----				
6				-----	-----	-----	-----				
7				-----	-----	-----	-----				
8											
9											

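### The Cohort A cycle 1 diary asks for a call at systolic above 150, but Table 3 treats persistent systolic from 140, and no provider reading is scheduled from C1D8 to C2D1

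*Combined protocol and SAP*

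**What the plan says.** **The diary.** Appendix E, instruction 7, asks patients to measure their pressure at home at least daily. The first step is "If your systolic pressure (top number) is greater than 150 or your diastolic blood pressure (bottom number) is greater than 90, re-measure", with the repeat taken 1 to 4 hours later. The call rule is "If your systolic pressure is still greater than 150 or your diastolic blood pressure is still greater than 90, please contact" the study team. Separately, "You should also call the research team if you experience any symptoms of high blood pressure". Instruction 6 has the patient bring the form and "tablets when you return for each appointment". Section 5 has the diary handed in at the end of each cycle.

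**The management table.** Table 3 in Section 6.1.5 defines the treatment band as "Persistent Grade 2-Moderate Systolic 140-159 Diastolic 90-99". Its first step is "Initiate BP treatment and if needed, after 24-48 hr of treatment, increase dose in stepwise fashion every 24-48 hours". The next band, where pazopanib is held, is "Persistent Grade 3 Severe Systolic ≥ 160 Diastolic ≥ 100". The notes under the table refer to "early initiation of antihypertensive treatment for grade 1 or 2 hypertension to minimize more severe or persistent hypertension".

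**The provider schedule.** In the expansion phase, Sections 5 and 6.1.5 and footnote c of the Section 10.2 calendar place provider readings on days 1 and 8 of cycle 1, then at the start of each later cycle. The calendar marks no vital signs in weeks 3 or 4 of cycle 1. The dose escalation phase has provider readings every 2 weeks over the first two cycles.

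**The concern.** The diary and Table 3 agree on diastolic pressure, apart from a reading of exactly 90, but not on systolic. Between C1D8 and C2D1, home readings are the only scheduled blood pressure surveillance in Cohort A, so the diary threshold decides whether staff hear about Grade 2 hypertension in time to treat it as Table 3 directs.

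Hypertension is an expected toxicity here. Section 2.2 reports it in 40% of pazopanib patients in the phase 3 renal cell trial, and cites 30 serious hypertension events and 3 hypertensive crises across pazopanib trials. Section 6.1.9 calls it a common risk factor for reversible posterior leukoencephalopathy. The protocol presents early treatment as the way to prevent more severe or persistent hypertension, and the diary trigger can delay that treatment.

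**Working it through.** The plan gives no figure to reproduce. The check compares the two thresholds and counts the days between scheduled readings.

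**Thresholds side by side (mmHg)**

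| | Systolic | Diastolic | Source |
|---|---|---|---|
| Eligibility limit | 140 | 90 | 3.1.11 |
| Table 3 Grade 2, start treatment if persistent | 140-159 | 90-99 | 6.1.5 |
| Diary re-measure and call | above 150 | above 90 | Appendix E, instruction 7 |
| Table 3 Grade 3, hold pazopanib | 160 or more | 100 or more | 6.1.5 |

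- Systolic gap between the treatment floor and the call trigger: 150 − 140 = 10.
- Margin from the call trigger to the Grade 3 hold: 160 − 150 = 10.
- In whole mmHg, the Grade 2 systolic band has 159 − 140 + 1 = 20 values. The diary is silent on 140 to 150, which is 150 − 140 + 1 = 11 of them, unless diastolic exceeds 90 or symptoms occur. This counts values on the scale, not patients.
- Diastolic: the rules differ only at exactly 90.

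**Days without a scheduled provider reading**

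- Cycles last 28 days, so C2D1 is day 29. From C1D8: 29 − 8 = 21 days.
- Section 10 allows the pre-cycle examination up to 3 days early. If pressure is taken then: 21 − 3 = 18 days.
- Section 10 also allows cycle 2 to start up to 1 week late: 21 + 7 = 28 days.
- Escalation phase, for comparison: 14 days.

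**Does the week-3 blood draw close the gap?** Laboratory tests fall in week 3 of cycle 1 (D15-21). Suppose staff read the diary at that visit, which the protocol does not require. The longest remaining interval is then the larger of (draw day − 8) and (29 − draw day):

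- D15: max(7, 14) = 14
- D18: max(10, 11) = 11
- D21: max(13, 8) = 13

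The range is 11 to 14 days, against Table 3's treatment steps of 24-48 hours.

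**Do other provisions cover it?** Section 5 says who may take a mid-cycle reading but schedules none for the expansion phase, and the expansion calendar footnote omits the mid-cycle line found in the escalation footnote. The notes to Table 3 require clinic readings for holding or reducing pazopanib. They do not require them for starting antihypertensives, so home readings could be acted on if the patient were prompted to call.

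**The case against.** The best defence is that the two thresholds do different jobs. Table 3 guides clinicians on persistent hypertension, while the diary is a call trigger for noisy home readings, and nothing in the protocol says they must match. A trigger above 150 still precedes the Grade 3 hold. However, a deliberate allowance for home-reading noise would be expected to raise both limits. Only the systolic limit was raised; the diastolic limit stays at 90, and no reason is given.

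Several limiting points stand:

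- The affected group is narrow (systolic 140-150, diastolic 90 or less, no symptoms, persistent), and its size cannot be estimated from the documents.
- Table 3 does not define persistence, so one reading of 140-150 would not by itself require treatment.
- Hypertension is treated mainly as a pazopanib effect, and the C1D8 reading comes after seven days of pazopanib. Later-onset cases remain exposed.
- The patient brings the diary to appointments, so an elevated reading could be noticed in week 3. That would be chance, since no reading or diary review is specified there.
- The effect on the trial's conclusions is small. The MTD is set before Cohort A opens, the second biopsy precedes the window, and daily readings make onset recoverable.

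A trigger at 140/90 could also draw calls from patients who entered at exactly the eligibility limit. Those values already fall in Table 3's Grade 2 band, so this is a cost of the change rather than an error in it.

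**Conclusion.** The concern holds. The diary's systolic trigger is 10 mmHg above the protocol's own treatment floor, during a nominal 21 days (about 18 to 28 with the permitted scheduling latitude) in which no provider reading is planned. The consequence is possible late treatment of a common and treatable toxicity. It does not mean missed detection or a threat to the trial's endpoints. The change should be made because the mismatch is clear and the remedy cheap.

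This conclusion applies to the Cohort A cycle 1 diary, the only form in the document. It assumes that no reading or diary review beyond the written schedule takes place between C1D8 and C2D1.

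**What to change.** In Appendix E, instruction 7, set both the re-measure and the call trigger at systolic 140 or more or diastolic 90 or more, matching the Grade 2 floor in Table 3. Keep the repeat reading 1 to 4 hours later and the symptom trigger as they are. The whole Grade 2 band then prompts contact.

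The cost is one revised diary page and some additional calls, mainly from patients who enter close to 140/90; the repeat reading limits these. No visits or measurements are added.

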APPENDIX F: LVEF DOSE MODIFICATION TABLE

Asymptomatic Decrease in LVEF

The decision to continue or hold STUDY DRUG is based on the LVEF as it relates to the institutions’s lower limit of normal (LLN) **and** change in ejection fraction from screening (LVEF as measured at registration) according to the following table:

Relationship of LVEF to institution’s LLN	LVEF Decrease < 10%	LVEF Decrease 10-15%	LVEF Decrease ≥ 16%
Normal	Continue	Continue	Continue and repeat MUGA/ECHO within 1-2 cycles
1-5% below LLN	Continue and repeat MUGA/ECHO within 1-2 cycles	Continue and repeat MUGA/ECHO within 1-2 cycles	HOLD and repeat MUGA/ECHO within 1-2 cycles
≥ 6% below LLN	Continue and repeat MUGA/ECHO within 1-2 cycles	HOLD and repeat MUGA/ECHO within 1-2 cycles	HOLD and repeat MUGA/ECHO within 1-2 cycles

Discontinue STUDY DRUG if:

- Two consecutive HOLD categories occur.
- Three intermittent HOLD categories occur (at the discretion of the investigator, STUDY DRUG may also be permanently discontinued prior to the occurrence of 3 intermittent HOLD categories).

If LVEF is maintained at a “Continue and repeat MUGA/ECHO” or improves from a HOLD to a “Continue and repeat MUGA/ECHO” category, additional MUGA scans/echocardiograms prior to the next scheduled MUGA/ECHO will be at the discretion of the investigator.

Symptomatic Cardiac Events

CTEP Protocol #8880
Clinical Center Protocol #: 12-C-0009

Discontinue STUDY DRUG if:

- A patient has symptoms of congestive heart failure (CHF) and a diagnosis of CHF is confirmed.
- A patient has a myocardial infarction.

APPENDIX G: FACSIMILE TRANSMISSION FORM FOR SAMPLE SHIPMENT

Please use this form to send notification of shipment

From:		Telephone:	
Date:		Fax:	

To: PPD

Fax:

Protocol Number:	
Number of samples shipped:	
Date Shipped:	
Expected date of arrival:	
Courier:	
Airway Bill No.:	
Number of packages:	
On dry ice:	Yes / No (Circle one)
Associated hazards:	
Shipped by: (Study Centre Number)	

CTEP Protocol #8880
Clinical Center Protocol #: 12-C-0009

Please use this form to send notification of shipment

From:		Telephone:	
Date:		Fax:	

To: Covance Inc.

Fax:

Protocol Number:	
Number of samples shipped:	
Date Shipped:	
Expected date of arrival:	
Courier:	
Airway Bill No.:	
Number of packages:	
On dry ice:	Yes / No (Circle one)
Associated hazards:	
Shipped by: (Study Centre Number)
